# **STUDY SUMMARY**

STUDY TITLE	Adipocytokines and their relationship with		
	obesity and endometrial cancer		
SHORT TITLE	Adipocytokines in endometrial cancer		
STUDY DESIGN	exploratory biomarker study		
STUDY PARTICIPANTS	Study population - patients presenting to		
	Royal Surrey NHS Foundation Trust with		
	endometrial cancer, identified at the MDT		
	Control population - female patients		
	without endometrial cancer, referred for		
	benign condition.		
PLANNED SIZE OF SAMPLE	100-120		
FOLLOW UP DURATION	N/A		
PLANNED STUDY PERIOD	36-48 months		
RESEARCH QUESTION /AIM(S)	To investigate the relationship between		
	adipocytokine level in blood and tissue		
	(endometrial cancer tissue, adipose tissue		
	and lymph node) in patients with		
	endometrial cancer and co-relate with BMI		
	to identify peripheral biomarkers that can		
	be used as prognostic or diagnostic tools		

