#### 3. THEORITICAL FRAMEWORK

As the incidence of endometrial cancer continues to rise there is a health need for a better diagnostic and prognostic approach.

Studying the different biomarker levels in blood and cancer tissue will enable us to look for new targets that may be useful in the treatment and prognostication of this cancer.

Also, if the levels of these markers change significantly post-treatment, we can investigate if it will be possible to use these markers to assess response to treatment as follow-up for risk of recurrence forms an important part of the treatment protocol.

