### 5. STUDY DESIGN and METHODS of DATA COLLECTION AND DATA ANALYSIS

# 5.1. Study design

All patients being referred to the Royal Surrey NHS Foundation Trust with diagnosed uterine cancer will be given the research information leaflet and invited to participate as the study

population of the research. Female patients being referred to Royal Surrey NHS foundation Trust for benign conditions (specifically not endometrial cancer) will be invited to participate as the control population.

Initially, an invitation letter will be sent alongside the patients' clinic appointment letter to inform them of the study and give them time for preliminary consideration of the study. Patients will then be approached in the outpatients' clinics after the initial consultation by the clinician. Alternatively, patients may be approached over phone and information about the study given at that time. The call will be scheduled after the clinic appointment visit so that the patient will have received the Invitation Letter that is sent out with the initial Appointment Letter, allowing patients sufficient time to consider the study. Patients will be given a participant information leaflet detailing the study rationale, methodology and analysis in clinic or alternatively the leaflet will be sent by post/ email (in case of telephone consultations). Patients who agree to participate in the study will be asked to sign a consent form after explanation at a later appointment.

Demographic data will be collected at the same time to correlate various risk factors associated with the development of uterine cancer. The data collected will include age, parity, smoking status, menopausal status, medications used, use of Hormone Replacement Therapy (HRT)/ hormonal contraception, and prevalence of diabetes and hypertension. This data will be collected by:

- Taking a medical history from the patient in clinic
- Patients' medical notes

This data will be directly entered into an existing departmental database for Gynaecological oncology which is password protected and stored on NHS computers.

Study participants will then have 30mls (2 ½ tablespoons) of venous blood taken on the day of the surgery and control participants will also have 30mls of venous blood collection alongside their clinic appointment.

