#### 6. STUDY SETTING

Study patients will be recruited when attending a clinic in the department of Gynaecological Oncology at Royal Surrey NHS Foundation Trust. Private consultation rooms are available here for discussing the study, history taking and consenting.

Blood sample will be collected on the day of the surgery when they are in the theatres and then repeated on day 1 post-operative in gynaecology ward and at 3 or 6 months post-surgery follow-up in clinic.

Tissue samples will be obtained from the following areas:

- 1. Adipose tissue from the main theatres at Royal Surrey NHS Foundation Trust
- 2. Uterine cancer tissue and lymph node from the histopathology department after they have finished analysis.

For those women recruited undergoing chemotherapy, blood sample will be procured at initial consultation and after 3rd (with the blood test before the fourth cycle of chemotherapy) and 6th cycles of chemotherapy. This can be performed in the Department of Gynaecological Oncology at Royal Surrey NHS Foundation Trust.

All samples (blood and tissue) will then be transferred to the Leggett Building at University of Surrey for processing and storage following HTA regulations. The samples will be double boxed for transfer. The outside box will be an icebox. The PI will personally transport the tissues by foot from the hospital to the Leggett building as they are very near geographically and it is a short 4 minutes' walk.

Control patients will be recruited when they attend a clinic appointment at Royal Surrey NHS Foundation Trust for any benign condition. Blood sample will be collected during their clinic appointment after written consent. If they are having any uterine surgery, endometrial tissue will be collected after histopathological diagnosis from the histo-pathology department.

Samples will also be stored anonymised (in case of patients who give consent) in Leggett building, University of Surrey following all regulations by HTA) for use in ethics approved future research project.

Historical samples / tissue blocks stored in the oncology department in the Leggett building, University of Surrey, from a previous study will also be used if appropriate consent is in place.

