### 7.1. Inclusion criteria

- 1. Study population- Women diagnosed with endometrial cancer
- 2. Control population Women being seen in clinic for benign conditions
- 3. Age 18 or above
- 4. Of sound mind so they can give informed consent
- 5. Historical tissue sample/ blocks from previous cases in the oncology department in the Leggett building also be used if appropriate consent is in place.

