# 7.4.1. Sample identification

Patients diagnosed with endometrial cancer will be identified through the Gynaecological Oncology Multi-Disciplinary Team meeting or by the Gynaecological Oncology or Medical Oncology teams. Control population will be identified through the above route or from referral letters to Royal Surrey NHS Foundation Trust.

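### The summary hopes for diagnostic markers, but the only case-control comparison sets diagnosed cancers against women with any benign condition, so its discrimination cannot be assumed to hold in women under investigation

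*Combined protocol and SAP*

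**What the plan says.** The diagnostic purpose appears in the Study Summary, where the markers sought are ones that could "be used as prognostic or diagnostic tools", and in section 3, which says "there is a health need for a better diagnostic and prognostic approach". The Study Summary also labels the work an "exploratory biomarker study".

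Cases enter after diagnosis. Section 7.1 lists "Study population- Women diagnosed with endometrial cancer", and section 7.4.1 adds that "Patients diagnosed with endometrial cancer will be identified through the Gynaecological Oncology Multi-Disciplinary Team meeting" or by the oncology teams. Archived samples from an earlier study may be added (sections 5.1 and 7.3).

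Controls are defined broadly. Section 5.1 describes them as "Female patients being referred to Royal Surrey NHS foundation Trust for benign conditions (specifically not endometrial cancer"), and section 6 says "Control patients will be recruited when they attend a clinic appointment at Royal Surrey NHS Foundation Trust for any benign condition". Section 7.2 excludes only women under 18 and those who cannot or do not consent. On how controls are found, section 7.4.1 says "Control population will be identified through the above route or from referral letters to Royal Surrey NHS Foundation Trust".

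The data items named in section 5.1 are age, parity, smoking, menopausal status, medications, hormone use, diabetes and hypertension. Reason for referral is not among them. Section 5.5 says only that results will be compared between the two populations.

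**The concern.** A diagnostic blood marker is naturally used in women in whom the disease is in question, to separate those who have it from those who do not. The comparison planned here is a different one: established cancers on one side, benign attendances of any kind on the other.

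Benign women who were investigated for endometrial cancer may resemble the cases more closely than other benign attenders do, for example in body weight. Sections 1 and 4.2 themselves tie these markers to obesity and inflammation. A marker could therefore separate the two recruited groups well and separate women under investigation less well. A larger sample or an added ROC analysis would not settle this, because the uncertainty lies in who the comparators are.

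At stake is what the study may conclude. If the case-control difference is read as evidence for a diagnostic tool, the reading goes beyond the comparison made, and the plan as written gives no means of picking out the controls who would be relevant.

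**Working it through.** **Plan's own figures.** The plan gives no AUC, sensitivity, specificity, effect size or SD, so there is no diagnostic figure to reproduce. The only related numbers are the group sizes in section 7.3: 30-60 cases, as many controls, total 100-120. At 1:1, 2 × 60 = 120 matches the upper end. 2 × 30 = 60 does not match the lower end, since 100 would need 50 cases. That mismatch is a separate matter; the sizes are used here only for precision.

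**Step 1: is the relevant comparison anywhere in the plan?**
- Cases: cancer already diagnosed (sections 5.1, 7.1, 7.4.1).
- Controls: any benign condition, with no requirement for symptoms, suspicion or work-up (sections 5.1, 6, 7.1, 7.2). Endometrial tissue is taken only if a control has uterine surgery (section 5.1).
- Some controls may come through the oncology route (section 7.4.1), so some may have been investigated. Nothing records which ones.
- Analysis: one undivided case-control comparison (section 5.5).

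The relevant subset may exist, but it cannot be identified from the listed data items.

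**Step 2: how far could the choice of comparator matter?** Every input in this step is an assumption; none comes from the documents. Take a normally distributed marker with equal variances, higher in cases, and a case-control gap of d = 0.8 SD. Let s be the distance by which benign women under investigation sit closer to the cases (negative means further away).

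- AUC = Φ((d − s)/√2)
- For a cut-off with 80% specificity in the recruited controls, specificity among women under investigation = Φ(0.842 − s)

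| s (SD) | (d − s)/√2 | AUC | Specificity |
|---|---|---|---|
| −0.2 | 0.707 | 0.76 | 85% |
| 0 | 0.566 | 0.71 | 80% |
| 0.2 | 0.424 | 0.66 | 74% |
| 0.4 | 0.283 | 0.61 | 67% |
| 0.6 | 0.141 | 0.56 | 60% |

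**Step 3: precision, including the cost of using a subset.** The Hanley-McNeil standard error is

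SE² = [A(1 − A) + (n₁ − 1)(Q₁ − A²) + (n₂ − 1)(Q₂ − A²)]/(n₁n₂),

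with n₁ cases, n₂ controls, Q₁ = A/(2 − A) and Q₂ = 2A²/(1 + A). For A = 0.714, Q₁ = 0.555, Q₂ = 0.595 and A² = 0.510. The 95% half-width, 1.96 × SE, is:
- 30 per group: 0.13
- 50 per group: 0.10
- 60 per group: 0.09
- 60 cases and 15 controls (assuming a quarter of 60 controls were investigated): SE = 0.067, half-width 0.13

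Under that assumption, restricting to the relevant quarter of controls costs about as much precision as shrinking the study from 60 to 30 per group.

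**The case against.** The strongest reply is that this is an exploratory study and that comparing known cases with non-cases is an accepted first step in finding candidate markers; evaluation in women with suspected disease usually comes later. The objective in 4.1 and the outcomes in 4.2 and 4.3 include no diagnostic-accuracy outcome, and section 5.5 includes no accuracy analysis. The case-control outcome in 4.2 is a comparison of marker levels, which this design can address. All of that stands, and it limits the point to what may be claimed from the comparison. It does not remove the point, because the Study Summary keeps the diagnostic aim, no limit on diagnostic inference is stated, and no later validation is planned.

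Four stronger readings are tempting, and the documents do not support them.
- *The plan formally tests a diagnostic aim on the wrong women.* It does not test that aim; diagnosis is a hoped-for use and a motivation.
- *Performance will fail to carry over, or the gap will be smaller.* The documents fix neither the size nor the direction of any difference, and the AUC could also rise.
- *The controls are not women in whom cancer was in question.* Section 7.4.1 lets controls come through the oncology route, so some may have been.
- *The protocol names suspected-cancer referrals as the intended users.* It does not; that is the natural reading of a diagnostic tool.

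It may also seem right to fill control places first with women referred for suspected endometrial cancer. That would shift the control definition in section 5.1 and might not suit the association aim. Benign status might also be unknown when blood is drawn in clinic. It is a trade-off, and the point does not depend on it.

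**Conclusion.** The point holds in a limited form. The planned comparison can describe how marker levels differ between diagnosed cases and benign attenders. It cannot support a statement about diagnosis among women being investigated for endometrial cancer, because the controls who would bear on that question are neither required nor identifiable.

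No size follows from the documents. The illustrated AUC range of 0.56 to 0.76 around 0.71 rests wholly on the assumed 0.8 SD gap, the assumed shifts of +0.6 to −0.2 SD and the equal-variance normal model. It shows that the comparator can matter; it does not estimate a bias in this study. The conclusion also rests on reading the intended use as women with suspected disease.

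This is a cheap improvement, not a flaw in the study's main comparison of marker levels.

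**What to change.** 1. **Section 5.1, data items.** For each control, add the reason for referral and whether endometrial cancer was investigated and excluded. Take both from the referral letter or the medical notes. Not every control is found through a referral letter, but section 5.1 already names the notes as a source. Complete the second item once the work-up has finished, since the result may not be known at the clinic blood draw.
2. **Section 5.5, analysis.** Report the case-control comparison separately for controls investigated for suspected endometrial cancer and for all other controls. Base any diagnostic statement on the first group only, and use the others for association only.
3. **Label any diagnostic statement hypothesis-generating.** Even with the relevant controls, cases are still women already diagnosed, and section 6 has surgical cases bled in theatre and controls in clinic.
4. **Study Summary, aim.** If the first group is too small to be informative, remove the word diagnostic. Set that minimum before marker results are seen.

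Leave the order in which controls are recruited unchanged.

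The cost is one short addition to the control data form, an analysis rule, and the amendment step in section 8.3 where it applies. The downside is wider intervals for any diagnostic statement, as the 15-control illustration shows.

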### 5.5. Data analysis

Standard statistical analytical tools will be used to analyse the data. Relation between different variables will be sought with odds ratio, confidence interval and significance with P value (<0.05 significant). The Mann–Whitney U test will be used to assess differential expression of immune markers between tissue types –blood and tumour tissue. Correlation with clinical characteristics will be determined using univariate log-rank and multivariable Cox proportional hazards adjusting for age, stage, grade and histology. Results will be compared between the study and the control populations.

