# 7.3. Sample size

We will aim to recruit 30-60 patients with diagnosed endometrial cancer in the study. This sample size will also include archived tissue sample (formerly consented and stored in Leggett building for use in future ethical research). We will aim to recruit as many patients in the control population as in the study population, aiming for a total (study + control population) of 100-120 patients.

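### The summary aims at diagnostic tools, but section 5.5 plans only association measures: nothing measures discrimination or sets it beside age and BMI

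*Combined protocol and SAP*

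**What the plan says.** The study summary labels the design an "exploratory biomarker study". Its research question is how adipocytokine levels in blood and tissue relate to endometrial cancer and BMI, with the purpose of finding peripheral markers that could "be used as prognostic or diagnostic tools". Section 3 also cites a need for better diagnosis and prognosis. In section 4.2 the first primary outcome compares marker levels between cancer patients and controls, and the third relates the markers to WHO category of BMI after adjustment.

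Section 5.5 is the whole analysis plan:

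- "Relation between different variables will be sought with odds ratio, confidence interval and significance with P value (<0.05 significant" is the general method.
- "The Mann–Whitney U test will be used to assess differential expression of immune markers between tissue types", the types being blood and tumour.
- Clinical characteristics are examined by "univariate log-rank and multivariable Cox proportional hazards adjusting for age, stage, grade and histology".
- "Results will be compared between the study and the control populations", with no test or measure named.

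On numbers, section 7.3 says "We will aim to recruit 30-60 patients with diagnosed endometrial cancer in the study", with about as many controls and a total of 100-120. No ROC curve, AUC, sensitivity, specificity, predictive value, cut-off or minimum accuracy appears anywhere in the text.

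**The concern.** A P value for a group difference says whether two distributions differ. It does not say how far they overlap, which is what decides whether a marker could help diagnosis. A reader of the final report who wants to know whether a marker shows diagnostic promise would find no planned output that answers.

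BMI sharpens the point. The background in section 1 rests on obesity being related both to these markers and to the cancer. A difference between cases and controls could therefore largely restate BMI. Outcome 3 of section 4.2 would show that a marker tracks BMI, but not whether it separates cases from controls any better than age and BMI already do. The Cox model in section 5.5 adjusts for age, stage, grade and histology, so it does not address this either.

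At stake is interpretation: a significant but weakly discriminating marker could be read as supporting the diagnostic part of the aim.

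**Working it through.** **The plan's own figure.** The total of 100-120 cannot be reproduced, because no effect size, SD, power or target accuracy is given. At 1:1 it implies 50-60 per group. The stated 30-60 cases with equal controls would give 60-120, so a total of 100-120 with only 30 cases means 70-90 controls.

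**Inputs.** Group sizes follow from section 7.3 and the 0.05 level is from section 5.5. Two assumptions are added: a two-sided test (sidedness is not stated) and an unadjusted Mann-Whitney comparison of cases with controls (section 5.5 assigns that test to blood versus tumour tissue).

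**Step 1: smallest observed AUC that reaches P<0.05.** Since AUC = U/(n1 × n2), its standard error under no difference is sqrt((n1+n2+1)/(12 × n1 × n2)), and the threshold is 0.5 + 1.96 × SE. For 60/60: 0.5 + 1.96 × sqrt(121/43,200) = 0.5 + 1.96 × 0.0529 = 0.604.

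**Step 2: what that AUC means.** Under an equal-variance normal model the standardised difference is d = sqrt(2) × Φ⁻¹(AUC), and sensitivity at 90% specificity is Φ(d − 1.2816). For 60/60: d = 0.372 and Φ(−0.910) = 0.182.

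| Cases / controls | AUC at P=0.05 | d | Sensitivity at 90% specificity |
|---|---|---|---|
| 60 / 60 | 0.604 | 0.372 | 18.2% |
| 50 / 50 | 0.614 | 0.409 | 19.1% |
| 30 / 90 | 0.620 | 0.431 | 19.8% |
| 30 / 70 | 0.624 | 0.447 | 20.2% |

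**Step 3: does the choice of test matter?** Little. In simulated logistic regressions (1,500 data sets per size), which yield the odds ratios that section 5.5 names, the median AUC among results with P between 0.04 and 0.06 was 0.602 at 60/60 and 0.614 at 50/50. A median split gives the same picture. With 36/60 cases and 24/60 controls above the median, the odds ratio is (36 × 36)/(24 × 24) = 2.25 with P = 0.028, while the AUC is (0.60 + 0.60)/2 = 0.60.

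**Step 4: how often would a weak marker pass?** The step 1 figures are observed values at the boundary. A true AUC of 0.60 corresponds to d = 0.358. The chance of P<0.05 is about Φ(d/sqrt(1/n1 + 1/n2) − 1.96), which is 50% at 60/60 and 43% at 50/50.

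**Step 5: would a stricter P value cure it?** No. Bonferroni for six markers moves the AUC threshold only to 0.640 (60/60) or 0.653 (50/50).

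**Step 6: is AUC estimable here?** Yes, for single markers. By the Hanley-McNeil formula, the 95% half-width at an AUC of 0.80 is about 0.080 (60/60), 0.087 (50/50) and 0.103 (30/70).

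**The case against.** The strongest reply is that this is an exploratory study whose operative objective in section 4.1 is to assess relationships. None of the outcomes in sections 4.2 and 4.3 is diagnostic accuracy, and an association screen is a proper use of P values. This stands, and it is why the point is minor. It does not remove the mismatch, because the summary names diagnostic tools as a purpose and the comparison of cases with controls is a primary outcome.

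A reader might infer that the protocol will declare any marker with P<0.05 a diagnostic candidate. It does not say so: section 5.5 defines what counts as significant and contains no rule for taking a marker forward. Nor is P the only output, since a confidence interval, rank test, log-rank and Cox model are also listed. The sound criticism is that none of these, as planned, measures diagnostic discrimination.

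A reader might also want gain in AUC over age and BMI to be the deciding criterion. The design does not support that. Six markers plus age and BMI make eight parameters on 30-60 cases, or about 4 to 8 cases per parameter (30/8 to 60/8). Controls are unmatched women with unspecified benign conditions, so the AUC of age and BMI depends on who is recruited. Cases are bled on the day of surgery and controls in clinic, and archival serum is added. Any gain in AUC should therefore be descriptive.

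**Conclusion.** The point holds as a low-severity mismatch between aim and analysis. As planned, the outputs can support association but cannot speak to the diagnostic part of the aim, alone or relative to age and BMI. At the planned total, significance needs an observed AUC of only about 0.60-0.62, or roughly 18-20% sensitivity at 90% specificity.

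The size rests on a two-sided, unadjusted rank test, an equal-variance normal model for the sensitivities, and a blood sample from every counted case and control. Covariate adjustment would shift the threshold, and fewer blood samples would raise it.

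Two stronger readings are not supported. First, a marker with true AUC 0.60 would not reliably pass: it would do so about 43-50% of the time at 50-60 per group. Second, 30 versus 30 (threshold 0.647) follows from the lower end of the case range with equal controls, but it totals 60 and falls short of the stated 100-120.

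**What to change.** In section 5.5, for the comparison of cases with controls on each blood marker:

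- Report AUC with 95% CI.
- Set it beside the AUC of a model with age and BMI only, and of that model plus the marker. Present the gain descriptively.
- If a six-marker panel is reported, correct its AUC for optimism (for example by bootstrap) and label it exploratory.
- State that P<0.05 alone supports association only and that no diagnostic conclusion will be drawn from it.

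In section 5.1, add BMI to the data items for controls as well as cases. It is not named there, although section 4.2 needs it.

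No new patients, samples or assays are required. The cost is a little more analysis and one data item to confirm. The downsides are that gains in AUC will be imprecise at this size and results will look less favourable than P values alone.
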